#### 5.4 Withdrawal of Patient from the Trial or Study Drug

The Investigator may withdraw a patient from the study and/or from dosing for any of the following reasons. The Sponsor or its designee must be notified within 24 hours using the procedures outlined in Section 7.12:

- A violation of enrollment criteria or other significant protocol violation is discovered after a patient has enrolled and been treated,
- A serious, intolerable, or dose-limiting AE (as described in the DLT definitions above, Section 4.2) occurs,
- Patients who are symptomatic from, or require treatment for, SARS-CoV-2 active infection should be withdrawn from study drug. The Sponsor, in consultation with the investigator, may grant exceptions to this rule if the benefit:risk ratio of

continuing therapy with study drug outweighs the benefit:risk ratio of withdrawal from study drug (see Section 6.3),

- The Sponsor, Investigator, or regulatory agency terminates the study,
- The patient requests to be discontinued from the study,
- The Investigator, in his/her best medical judgment, decides that the patient should be withdrawn from the study or from dosing,
- If the patient becomes pregnant during the study, the patient must discontinue the study drug immediately. The health status of mother and child should be followed and reported after delivery,
- Patient has not achieved at least a PR (defined as decrease of bone marrow blast percentage to 5% to 25%, or decrease of pretreatment bone marrow blast percentage by at least 50%) following 2 cycles of flotetuzumab therapy,
- Patient with evidence of disease progression after achieving at least PR,
- Patient transitions to stem cell transplant.

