# 8.3.2 Follow-up Period

Follow-up information will be requested by the Sponsor after end of treatment until death or withdrawal of consent, but not beyond 2 years after the last patient is enrolled. All patients will have clinical information including safety, transfusion requirements, disease and vital status information collected during the follow-up period. Depending on treatment response, patients may be required to continue follow-up at the study site for the first 6 months post treatment. After these first 6 months, follow-up can be conducted outside of study site, but follow-up information must still be provided to Sponsor as outlined.

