Sensitivity analysis of OS and EFS: patients will be censored for alternative therapies or procedures such as surgery, HSCT, radiation and subsequent antileukemic therapy, etc. If a patient begins a subsequent antileukemic therapy prior to event, the patient will be censored at the date of last assessment before starting the new anti-cancer therapy. For EFS, patients with two or more consecutive missing response assessments prior to event will be censored at the last date of response assessment before the missing assessments.

Time to response (TTR) is defined as time from first dose of study drug to first CR, CRh, CRi (CRn, CRp), or MLFS and will be summarized with descriptive statistics. Time to CR/CRh and time to best overall response will be calculated.

Mortality rate is defined as rate of death from any cause within 30, 60, 90, or 180 days of first dose of study drug. Number and percentage of deaths at 30, 60, 90, or 180 days will be summarized.

Six-month survival rate is defined as the probability of survival at 6 months from first dose of study drug.

One-year survival rate is defined as the probability of survival at 1 year from first dose of study drug.

Six-month and one-year survival rates will be evaluated by KM estimate with 95% CI.

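### Mortality at 30 to 180 days is a crude percentage with no denominator or unknown-status rule, and the protocol disagrees with itself on vital-status follow-up after withdrawal

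*SAP*

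**What the plan says.** **Withdrawal.** Protocol 5.4 opens a single list with "The Investigator may withdraw a patient from the study and/or from dosing for any of the following reasons". Among the reasons are a dose-limiting adverse event, failure to reach PR "following 2 cycles of flotetuzumab therapy", "Patient with evidence of disease progression after achieving at least PR", and transition to transplant. The list does not separate reasons for stopping drug from reasons for leaving the study.

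**Follow-up.** Protocol 8.3.2 states: "Follow-up information will be requested by the Sponsor after end of treatment until death or withdrawal of consent", with a cap of two years after the last enrolment. It collects progression date, transplant status and death for every patient at each follow-up; non-responders are contacted every three months. Protocol 9.6.1 and SAP 11.1 require at least six months of follow-up, or death, for all treated patients before the 100- and 170-patient cutoffs. Protocol 4.4 defines the end of the trial by following the last patient only to progression, transplant, consent withdrawal or death.

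**Estimators.** SAP 11.2.2 says of early mortality: "Number and percentage of deaths at 30, 60, 90, or 180 days will be summarized". Of the survival rates it says: "Six-month and one-year survival rates will be evaluated by KM estimate with 95% CI". For overall survival it censors patients of unknown status when last known alive. SAP 7.2 says that missing data are handled as missing in summaries.

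**The concern.** An investigator who uses 5.4 to take a patient off study at non-response or progression may end vital-status collection in someone at high risk of death. Protocol 7.11.1 confirms that this route ends observation. A patient whose drug is stopped for a related event stays under observation unless the investigator has withdrawn that patient from the study.

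The SAP foresees unknown vital status, because it censors it for overall survival. It has no counterpart for the mortality percentages. The report could then carry two results for almost the same time point, 180-day mortality and six-month survival, that disagree for no reason other than the handling of the same patients. Early mortality is a stated secondary objective, and in a single-arm trial there is no control group to share the bias.

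**Working it through.** **Plan's own figure.** The documents state no mortality rate, no loss rate and no expected precision for mortality, so there is nothing to reproduce on this point. The sizes below rest on assumed inputs.

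**Step 1: the follow-up passages side by side.**
- 5.4: study withdrawal is permitted at non-response, progression after at least PR, dose-limiting toxicity or transplant.
- 4.4: the last patient is followed to progression or transplant, if these come before death.
- 8.3.2: follow-up runs "after end of treatment until death or withdrawal of consent", for all patients.
- 9.6.1 and SAP 11.1: six months or death before the two main cutoffs, with no statement about patients already withdrawn under 5.4.

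The first two cannot both be applied as written with the third.

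**Step 2: what each denominator does.** Take N = 170 (SAP 4.2) and, for illustration, assume 60 known deaths by day 180 and 17 patients of unknown status.
- Unknowns kept and not counted as deaths: 60/170 = 35.3%.
- Unknowns dropped: 60/(170 − 17) = 60/153 = 39.2%.
- Unknowns all dead: (60 + 17)/170 = 45.3%.

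If the unknowns have true death probability q, the truth is (60 + 17q)/170. The first figure is low by 17q/170 = 0.1q, whatever q is. The second is too high when q is below 60/153 = 39.2% and too low when q is above it.

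**Step 3: size under independent loss.** Let m be true 180-day mortality and l the cumulative loss by day 180 in the absence of death, both with constant hazards: a = −ln(1 − m)/180 and b = −ln(1 − l)/180. Then at day 180:
- expected deaths/N = [a/(a + b)] × [1 − (1 − m)(1 − l)];
- expected unknown/N = [b/(a + b)] × [1 − (1 − m)(1 − l)];
- Kaplan-Meier recovers m.

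Worked case, m = 40%, l = 10%: a/(a + b) = 0.5108/(0.5108 + 0.1054) = 0.829, and 1 − 0.6 × 0.9 = 0.46. Deaths/N = 0.829 × 0.46 = 38.1%, unknown/N = 7.9%, and deaths over known status = 0.381/0.921 = 41.4%.

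| m | l | Deaths/N (gap, points) | Unknowns dropped (gap, points) |
|---|---|---|---|
| 30% | 2% | 29.7% (−0.3) | 30.2% (+0.2) |
| 30% | 10% | 28.6% (−1.4) | 31.2% (+1.2) |
| 40% | 10% | 38.1% (−1.9) | 41.4% (+1.4) |
| 40% | 20% | 36.2% (−3.8) | 43.0% (+3.0) |
| 50% | 30% | 42.9% (−7.1) | 55.1% (+5.1) |

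In 170 patients, gaps of 0.3, 1.9 and 7.1 points are about 0.5, 3 and 12 uncounted deaths (170 × 0.003, 0.019, 0.071).

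**Step 4: by time point.** With m = 40% and l = 10%, the downward gap is 0.1, 0.3, 0.6 and 1.9 points at days 30, 60, 90 and 180. The non-response trigger falls after two 28-day cycles, about day 56. It cannot touch day 30 and can hardly touch day 60. Before then, only withdrawals for other reasons, such as toxicity or investigator judgment, could matter.

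**The case against.** The strongest defence is that follow-up is already specified. Section 8.3.2 covers all patients, names non-responders, and collects transplant and progression data, which would make little sense if those events ended follow-up. The six-month minimum in 9.6.1 and SAP 11.1 has no exception. On this view the wording in 5.4 is only a shared list for two different actions, and 4.4 only defines when the trial closes. This largely stands as evidence of intent and limits the likely number of unknowns. It does not remove the conflict, since no passage says what happens to vital status once 5.4 has been used to take a patient off study.

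A reader might infer that the SAP counts patients of unknown status as alive and so flatters the drug. No passage says so. Deaths over population size is the natural reading, because SAP 11.2 summarises secondary endpoints in named populations with exact intervals. But SAP 7.2 could equally mean exclusion, and under independent loss that reverses the sign.

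A reader might also multiply an assumed 20% unknown by an assumed 70% chance of death and reach 14 points. The documents give neither figure, the product holds only under the first denominator, and 20% unknown sits badly with the planned follow-up.

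Finally, mortality is an additional rather than a key secondary endpoint, and six-month survival by Kaplan-Meier is already planned. Both are true. They make the change cheap and do not justify reporting a second, inconsistent figure.

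**Conclusion.** The point holds in limited form. Sections 5.4 and 4.4 conflict with 8.3.2 on whether vital status is followed after withdrawal, progression or transplant, and SAP 11.2.2 leaves the mortality percentage without a denominator or unknown-status rule.

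At day 180 the bias is downward by about 0.3 to 7 points if unknowns stay in the denominator. If they are dropped, it is upward by about 0.2 to 5 points. Both ranges assume 30-50% mortality, 2-30% cumulative loss and loss unrelated to prognosis. If withdrawal selects patients at higher risk, the upward bias shrinks and may turn downward. The effect is small at days 30 to 90 and zero if vital status is complete. The documents do not support a firm direction, a material effect on 30-day mortality, or any effect on the primary CR/CRh test, its alpha or its power. The change is worth making because the present text allows two conflicting results for one quantity.

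**What to change.** 1. In SAP 11.2.2, report mortality at days 30, 60, 90 and 180 as 1 minus the Kaplan-Meier estimate with a 95% confidence interval, in the stated population. Show beside it the raw number of deaths and the number of patients of unknown status at each day.
2. Reconcile Protocol 5.4, 4.4 and 8.3.2 so that stopping study drug does not by itself end the vital-status follow-up that 8.3.2 already plans. No treatment-stopping criterion needs to change, and withdrawal from the study at the investigator's judgment can remain.

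The second change matters as much as the first. Kaplan-Meier assumes that censoring is unrelated to prognosis and cannot correct for withdrawal at progression; complete vital status can.

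The cost is about a sentence in the SAP and a wording clarification in the protocol, with no new visits. The downside for the sponsor is that reported mortality may be slightly less favourable.

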11.2.3 Other Secondary Analyses

Immunogenicity

Anti-drug antibody production will be monitored using a bridging ELISA method. The proportion of patients who become positive in this assay will be reported.

Pharmacokinetics

Serum concentrations of flotetuzumab will be monitored using an electrochemiluminescencebased sandwich assay. PK analyses will be performed using industry standard software. Population PK modeling will be performed, and an appropriate model and model parameters will be described. This analysis will be performed by an outside consultant.

Safety and Efficacy with Use of Tocilizumab

The number of patients who received tocilizumab in treatment of infusion related reaction (IRR) and or cytokine release syndrome (CRS) will be reported. The incidence, severity, and duration of IRR/CRS will be summarized and will be broken down by patients who received or not received tocilizumab.

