## 6.4.1.2 Management of Observed Flotetuzumab Infusion Reactions and Infusion-related Adverse Events

The following are treatment guidelines (which may be modified as needed by the responsible Investigator according to the best practices of medicine) for flotetuzumab IRRs including CRS. Early intervention at the first signs of IRR/CRS, including pyrexia, tachycardia, tachypnea and/or hypotension in the absence of alternative etiologies and in consistent temporal relationship to administration of flotetuzumab, should be undertaken. Through Amendment 4, IRR/CRS has been graded using CTCAE v4.0. Based on current understanding gained with patients treated with CAR-T cells (which have a T-cell activating mechanism of action in common with flotetuzumab), CRS is likely to be a common toxicity that can be managed through supportive care and anti-cytokine interventions to allow for full activity of T cells during therapy. An alternative grading scale for CRS proposed by Lee et al. (26) allows for more intensive supportive care and treatment of the underlying cause of the CRS (excessive cytokine production) before the event must be considered Grade 3 or Grade 4 severity. Adopting this definition of CRS as described in Table 5, and concomitantly modifying the guidelines for management of IRR/CRS (below) as implemented in Amendment 5 and further modified in Amendment 13, will allow for more flexible management of patients who develop CRS and who may nonetheless experience clinical benefit despite the need to manage through mild or moderate infusion reactions while not jeopardizing overall safety.

Infusion related reaction including CRS is a common toxicity with flotetuzumab, especially when the drug is initiated and dose escalated during lead-in dosing. Evaluate for and treat other causes of fever, hypoxia, and hypotension according to institutional best practices or guidelines. Initial IRR/CRS management with fluids and antipyretics is allowed as clinically indicated, per local institutional practices. Celecoxib (14), if platelet counts allow, may be considered for myalgia and arthralgia. If celecoxib is contraindicated consider the use of corticosteroids per Table 5, Grade 1 CRS. If CRS is suspected, refer to Table 5 for management guidelines or treat according to local institutional guidance. Every attempt should be made to continue the infusion during management of the reaction. The definitions for high-dose vasopressors are shown in Table 6.

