#### Table 5CRS Grading and Recommended Management Guidance

CRS Grade (26)	Dose Modification	Tocilizumab	Corticosteroids
Grade 1 Symptoms are not life threatening and require symptomatic treatment only, e.g., fever, nausea, fatigue, headache, myalgias, malaise	Slow infusion rate by 10-20%. After stabilization/resolution increase infusion rate as clinically indicated every 4-6 hours.	Administer tocilizumab (14) 8 mg/kg IV over 1 hour (not to exceed 800 mg/dose). If no clinical improvement in the signs and symptoms of CRS after the first dose, repeat tocilizumab every 8 hours as needed. Limit to a maximum of 3 doses in a 24-hour period; maximum total of 4 doses.	Administer dexamethasone (e.g., 4 to 6 mg IV or oral every 8 hours) for 24-48 hours.
Grade 2 Symptoms require and respond to moderate intervention Oxygen requirement < 40% or Hypotension responsive to fluids or low-dose of one vasopressor (Table 6) or Grade 2 organ toxicity	Slow infusion rate by 25-50%. After stabilization/resolution increase infusion rate as clinically indicated every 4-6 hours.	Per Grade 1	Manage per Grade 3 if no improvement or worsening within 24 hours after starting tocilizumab.
Grade 3 Symptoms require and respond to aggressive intervention Oxygen requirement ≥ 40% or Hypotension requiring high-dose vasopressors or multiple vasopressors (Table 6) or Grade 3 organ toxicity (except transaminitis) or Grade 4 transaminitis	Interrupt infusion, DO NOT FLUSH line. Aspirate residual drug from line. After resolution or stabilization to Grade 1 resume infusion at previous tolerated dose, and increase rate as clinically indicated every 4-6 hours.	Per Grade 1	Administer dexamethasone (e.g., 8 to 10 mg intravenously every 8 hours) or equivalent. Continue corticosteroid use until the event is Grade 1 or less, then taper over 3 days.

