## 7.11.4 Reporting of Adverse Events to the Sponsor

Adverse events and SAEs will be collected and followed from the time the patient provides informed consent for the study (see Section 8.1) through 28 days after the last administration of study drug or until the start of a subsequent systemic anticancer therapy, if earlier. If a patient experiences an AE after the informed consent document is signed and prior to treatment with study drug, it should be captured as medical history; however, if the Investigator believes the AE may have been caused by a protocol procedure, or related to ruxolitinib, it will be reported to the Sponsor or its designee and/or entered on the eCRF.

Adverse events occurring after the patient undergoes early termination or completes the trial (attains 28 days after last administration of study drug or starts a subsequent systemic anticancer therapy, if earlier) need not be reported unless the event is serious and the Investigator believes that the event may have been caused by the study drug or a protocol procedure.

To identify the occurrence of any new medical complaints or worsening of previous complaints, non-leading questioning should be posed to the patient.

Events related to leukemia progression/worsening of underlying disease (including those with a fatal outcome) will be collected as efficacy endpoints, and not documented as AEs/SAEs. However, if an SAE occurs in a patient and it is unclear if the event is due to progressive disease, the SAE should be reported.

If a patient reports signs and symptoms that represent a single medical syndrome, diagnosis, or concept, the syndrome/diagnosis/concept should be documented as an AE (e.g., cough, runny nose, fever = Upper Respiratory Tract Infection) in the eCRF. One exception is for IRR/CRS, for which the Sponsor would like to collect specific information on signs and symptoms. For IRR/CRS, report just the IRR/CRS event as an AE; signs and symptoms associated with IRR/CRS should only be reported on the IRR/CRS eCRF page and not as independent AEs.

The Investigator must follow all SAEs until resolution. Resolution of an event is defined as the return to pre-treatment status or stabilization of the condition with the expectation that it will remain chronic.

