# 9.7.3 Safety and Efficacy of Tocilizumab in Treatment of IRR/CRS

IRR/CRS events are captured as AESIs (see Section 7.11.3). The incidence, severity and duration of IRR/CRS events will be summarized in tables. Furthermore, safety with the use of tocilizumab will also be assessed.

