3.2 Secondary Objective(s)

Collectively, the secondary objectives of this study are:

- Assessment of CR rate, CRh rate, overall complete response rate (CR, CRh, CRi [CRn, CRp], or MLFS), objective response rate (CR, CRh, CRi [CRn, CRp], MLFS, or PR), time to response and duration of response (DOR).
- To measure early mortality rates, overall survival (OS) and event-free survival (EFS).
- To determine the rate of eligible patients, per institution criteria, that transition to successful stem cell transplant after achieving complete response (CR, CRh, CRi [CRn, CRp], or MLFS).
- To assess rate of conversion to and maintenance of transfusion independence.
- To evaluate duration of initial hospitalization for flotetuzumab administration.
- To evaluate incidence and duration of hospitalizations subsequent to initial discharge.
- To monitor the safety and tolerability of flotetuzumab.
- To characterize the PK and immunogenicity of flotetuzumab.
- To determine safety and efficacy of tocilizumab in the treatment of IRR/CRS.

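### The split of IRR/CRS by tocilizumab received or not received cannot show whether tocilizumab works, because the drug is given only once IRR/CRS has begun

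*SAP*

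**What the plan says.** SAP 3.2 lists as a secondary objective "To determine safety and efficacy of tocilizumab in the treatment of IRR/CRS", and Protocol 3.2 has the same objective. SAP 11.2.3, under its tocilizumab subheading, plans two things. The first is a count: "The number of patients who received tocilizumab in treatment of infusion related reaction (IRR) and or cytokine release syndrome (CRS) will be reported". The second is a breakdown: "The incidence, severity, and duration of IRR/CRS will be summarized and will be broken down by patients who received or not received tocilizumab".

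Protocol 9.7.3 summarises incidence, severity and duration of IRR/CRS without a split and adds "Furthermore, safety with the use of tocilizumab will also be assessed". Neither document plans an outcome measured from the first tocilizumab dose.

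The drug's role is set out in Protocol Table 5, which recommends it at Grade 1 and refers Grades 2 to 4 back to that entry. Repeat dosing depends on response: "If no clinical improvement in the signs and symptoms of CRS after the first dose, repeat tocilizumab every 8 hours as needed". Tocilizumab does not appear in Table 4, the premedication table. Protocol 6.4.1.2 describes the whole scheme as "treatment guidelines (which may be modified as needed by the responsible Investigator according to the best practices of medicine".

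**The concern.** A drug given because an event has occurred cannot be evaluated by asking whether the event occurred in those who received it. Incidence in the received column is settled before the first dose.

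Severity and duration have a related problem. Among patients with IRR/CRS, the investigator decides who is treated, probably in light of how the event is going. Short events may end before the drug is given. Duration also counts time that passed before dosing.

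At stake is a named secondary objective. Protocol 4.1.2 already credits lead-in dosing together with early tocilizumab with easing CRS in this trial. A reader who turns to the planned table for support will find a display that cannot supply it and could suggest the opposite.

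**Working it through.** The plan gives no rate, sample size or alpha for this objective, so there is no figure to reproduce. Every numerical input below is assumed for illustration; the documents supply none.

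**Step 1: incidence.** Let *i* be the overall proportion of patients with IRR/CRS and *r* the share of those given tocilizumab. Recipients are by definition treated for IRR/CRS, so their incidence is n/n = 100%. Incidence in non-recipients is *i*(1 − *r*)/(1 − *ir*).

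- *i* = 0.70, *r* = 0.60: 0.28/0.58 = 48%.
- *i* = 0.90, *r* = 0.60: 0.36/0.46 = 78%.
- *r* = 1 with *i* below 1 (every event treated, as a literal reading of Table 5 implies): 0%, leaving no untreated events to set beside the treated ones.

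No term for the drug's effect enters either expression.

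**Step 2: severity and duration with an inert drug.** Assume Grades 1 to 4 occur in proportions 0.45, 0.42, 0.10 and 0.03 of patients with IRR/CRS, with mean durations of 1, 2, 3 and 4 units.

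*Use rising with grade* (0.20, 0.60, 0.90, 0.95):

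- Share treated: 0.0900 + 0.2520 + 0.0900 + 0.0285 = 0.4605.
- Grade 3 or higher, recipients: 0.1185/0.4605 = 25.7%.
- Grade 3 or higher, non-recipients with IRR/CRS: 0.0115/0.5395 = 2.1%.
- Mean duration, recipients: (0.090 + 0.504 + 0.270 + 0.114)/0.4605 = 2.12.
- Mean duration, non-recipients with IRR/CRS: (0.360 + 0.336 + 0.030 + 0.006)/0.5395 = 1.36.

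*Use unrelated to grade* (0.60 throughout):

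- Grade 3 or higher is 13.0% in both groups, and mean duration is 0.45 + 0.84 + 0.30 + 0.12 = 1.71 in both.
- If the rows use all patients rather than those with IRR/CRS, then at *i* = 0.70 non-recipients show 0.70 × 0.13 × 0.40/0.58 = 6.3% against 13.0%.

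**Step 3: time before dosing.** Assume durations are exponential with mean 1 whether or not the patient is treated. Assume also that the time to dosing is exponential with mean *m*, and that the drug is given only if the event is still running. Mean duration is *m*/(1 + *m*) in non-recipients and 1 + *m*/(1 + *m*) in recipients. For *m* = 0.25, 0.5 and 1 this gives 0.20, 0.33 and 0.50 against 1.20, 1.33 and 1.50. Identical underlying durations look one unit apart.

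**Step 4: an effective drug.** Return to the rising-use case and suppose the drug halves total duration. Recipients show 2.12/2 = 1.06 against 1.36, an apparent ratio of 0.78 where the true ratio is 0.50. The sign is right here and the size is wrong.

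**Step 5: treatments given alongside.** Table 5 pairs tocilizumab with dexamethasone and a slowed infusion at Grade 1, and with an interrupted infusion at Grade 3. At Grade 2 the corticosteroid entry reads "Manage per Grade 3 if no improvement or worsening within 24 hours after starting tocilizumab". Even after restriction to patients with IRR/CRS, the columns would differ in more than tocilizumab.

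**The case against.** The strongest reply is that SAP 11.2.3 promises a descriptive breakdown, with no test, estimate or claim of effect. Tocilizumab appears in neither SAP Table 3 nor Table 4 and carries no alpha. The row denominator is not stated, and table shells are deferred to a separate programming plan (SAP 14). All of this stands and limits the weight of the point. It does not remove the gap, because the breakdown is the only analysis offered for an objective that names efficacy.

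A reader might go further and infer that the table will show more, worse and longer IRR/CRS with tocilizumab whether or not it works. The documents do not support that. Table 5 sets no grade threshold for tocilizumab, so any dependence on grade comes from investigator discretion, on which no data are given. Step 2 shows no gap among patients with IRR/CRS when use is unrelated to grade, and Step 4 shows an effective drug appearing effective. Nor can the untreated column be assumed to hold only mild events. Protocol 6.4.1.2 allows local institutional guidance, and the management guidance changed at Amendments 5 and 13.

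It is also fair to say that an account running from the first dose would be uncontrolled. That stands too, and is why the result must be labelled so.

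**Conclusion.** The point holds in limited form. The 100% incidence among recipients needs no assumption beyond the SAP's own definition of exposure as treatment for IRR/CRS. For severity and duration the right word is confounded: the sizes in Steps 2 and 3 rest wholly on assumed use patterns, and the direction is likely rather than certain.

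Either way, the planned split cannot answer the efficacy half of the objective and may mislead. The safety half can still be described. The effect is confined to one secondary objective; the primary CR/CRh test, the interim rules and the DLT monitoring are not touched.

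**What to change.** Amend SAP 11.2.3 as follows.

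- Remove incidence from the received/not-received split, and restrict the breakdown of severity and duration to patients with IRR/CRS.
- For treated events, describe time from first tocilizumab dose to resolution (in days if only dates are held) and the proportion needing repeat doses.
- Tabulate TEAEs with onset after the first tocilizumab dose.
- Report grade at dosing and later maximum grade only if the IRR/CRS form captures them. This is not assured: Protocol 4.2 grades the event as a whole, and Protocol 7.11.4 has one AE per event, adding that "signs and symptoms associated with IRR/CRS should only be reported on the IRR/CRS eCRF page".
- Report concurrent corticosteroid, vasopressor use, and slowing or interruption of the infusion as context, not as treatment failure.
- State that the result is descriptive and uncontrolled. Alternatively, reword the objective as describing tocilizumab use and outcomes.

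The cost is SAP wording and a few extra tables. Concomitant medications are already recorded (Protocol 6.6 and 7.3). The downside is that the trial will make no controlled statement about the efficacy of tocilizumab, which its single-arm design could not support in any case.
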